For logistical purposes, we are running this study in several phases. We have already begun the study in patients living within 20 miles of Miller-Keystone's Pittston Donor Center based on their home ZIP code recorded in their electronic health record. In collaboration with Miller-Keystone, we will create a plan for expanding the study to other geographic areas within Geisinger's service area.

For each geographic location where we run the study, we will first identify all patients from our list who meet our inclusion criteria above. Then, patients who have a blood type in need (A-, B-, AB-, O-, O+) will be randomized into the **3 shortage blood-type groups**.

A randomly-selected group of patients without a needed blood type will be selected from the patient list within that geographic area for a fourth **No-shortage control** group of the same size as each of the shortage groups listed above.

In order to encourage donation in as many patients with needed blood types as possible, we plan to send messages to those in the shortage control group at a delay (after the primary outcome time frame has passed). The patients in this group will also be randomized to receive either the no-blood-type or the blood-type message.

Planned analyses

Primary outcome

Number of Participants Who Attended a Donation Appointment

Attended a donation appointment within 6 weeks of their message send date, regardless of whether they donated. This outcome includes patients who were unable to donate for any reason (e.g., low hemoglobin) or patients who showed up to the appointment but decided to leave before donating.

[Time Frame: Within 6 weeks of the final message send date]

Question 1: Are patients who receive either message more likely to donate compared with patients who do not receive a message?

Analysis 1: We will test the hypothesis that patients who receive a message donate at higher rates than patients who do not receive a message by running an OLS regression with a binary predictor variable indicating whether or not patients were sent a message.

Question 2: Is blood donation higher in patients who receive a message that includes their blood type and mentions that their blood type is in need compared with a message that does not mention their blood type?

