1. Number of Participants Who Successfully Donated Blood

Attended a donation appointment within 6 weeks of their message send date and successfully donated, excluding patients who were turned away from or left their appointment without donating.

[Time Frame: Within 6 weeks of the final message send date]

2. Number of Participants Who Scheduled a Blood Donation Appointment

Scheduled an appointment within 2 weeks of their message send date.

[Time Frame: Within 2 weeks of the final message send date]

3. Number of Participants Who Scheduled a Blood Donation Appointment

Scheduled an appointment within 6 weeks of their message send date.

[Time Frame: Within 6 weeks of the final message send date]

Additional exploratory analyses

1. Household members

Patients who donate after receiving messages may also encourage members of their household to donate. We will run a negative binomial regression to test whether the number of donors residing at the same address as each target patient varies as a function of experimental group, whether the target patient donated or not, and the interaction between these variables.

2. First time donors vs. repeat donors

We will evaluate whether message effectiveness differs based on whether the patient has previously donated blood at Miller-Keystone. To this end, we will run an OLS regression model, testing whether donations vary as a function of experimental group, a bivariate indicator for whether or not the patient has previously donated blood, and the interaction between these variables.

3. Geographic location

Patients in certain geographic regions may be more receptive to our messages than others. We will test for differential effectiveness as a function of geographic region by running an OLS regression including a dummy coded predictor variable coding for geographic region (as defined by our separate outreach campaigns). We will test for an interaction between region and experimental group on donation behavior. If the interaction is significant, we will run post-hoc comparisons to probe for differences in the efficacy of our interventions separately by geographic region. If the interaction is not significant but the main effect of region is, we will run post-hoc tests on this main effect to understand how donation behavior differs by region.

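### The exploratory household model counts enrolled co-residents who were sent their own message, so influence running from them to the target distorts the group-by-donation interaction

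*SAP*

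**What the plan says.** Under Sample and randomization, the SAP says of each location that "we will first identify all patients from our list who meet our inclusion criteria above". It then says that "patients who have a blood type in need (A-, B-, AB-, O-, O+) will be randomized into the" three shortage groups: two messaged and one not. The no-shortage controls "will be selected from the patient list within that geographic area for a fourth" group. No limit of one patient per address and no allocation by household is stated.

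Under Additional exploratory analyses, item 1 (Household members), the premise is that "Patients who donate after receiving messages may also encourage members of their household to donate". A negative binomial regression will "test whether the number of donors residing at the same address as each target patient varies as a function of experimental group", with the target's own donation and its interaction with group also in the model. The count is not limited to residents outside the study or to residents without a message of their own.

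Shortage controls are messaged later: "we plan to send messages to those in the shortage control group at a delay (after the primary outcome time frame has passed").

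Analyses 1 and 2 classify each patient by the message that patient was sent. The checks under Sensitivity analyses and robustness checks concern message openers, early schedulers, patients near Danville, and logistic regression. None uses address.

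**The concern.** The household model is meant to show whether a messaged patient who donates brings others along. Its informative term is the interaction: household donors per donating target, messaged against control. That reading needs influence to run from target to co-resident.

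When the co-resident is also enrolled and was messaged, influence can run the other way. A control target then donates because of the co-resident, and enters the model as a control donor with one household donor. This fills the control-donor cell with pairs created by the message and shrinks the contrast that the analysis is looking for. An address with two enrolled patients also supplies two rows, in which each patient's donation is the outcome of one row and a predictor in the other.

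A secondary question is whether the same exposure disturbs Analyses 1 and 2, since a control can live with a messaged patient.

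**Working it through.** **The plan's own figure.** Project status gives at least 14,772 per arm, 1% against 1.35%, two-sided alpha 0.05, and 80% power. With mean rate 0.01175, the null standard error is √(0.01175 × 0.98825 × 2/14,772) = 0.001254, and the standard error under the alternative is also 0.001254. Power = Φ[(0.0035 − 1.96 × 0.001254)/0.001254] = Φ(0.83) = 79.7%. The stated power reproduces.

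**Household model: inputs.** From the SAP: rates of 1% (no message) and 1.35% (message); two of three randomised groups messaged, so an enrolled shortage co-resident is messaged with probability 2/3 if the groups are equal. Assumed: two enrolled shortage patients at the address, and each messaged donor brings a co-resident who would not otherwise donate with probability r = 0.3. Unmessaged donors bring nobody.

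*Control target*
- Target donates: 0.01 + 0.99 × (2/3) × 0.0135 × 0.3 = 0.012673.
- Both donate, co-resident messaged: 0.01 × 0.0135 + 0.99 × 0.0135 × 0.3 = 0.0041445. Co-resident not messaged: 0.01 × 0.01 = 0.0001.
- Both donate overall: (2/3) × 0.0041445 + (1/3) × 0.0001 = 0.0027963.
- Co-resident donation among control donors: 0.0027963/0.012673 = **22.1%**. With an unmessaged co-resident: 0.0001/0.01 = **1%**.

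*Messaged target*
- Target donates: (2/3) × (0.0135 + 0.9865 × 0.0135 × 0.3) + (1/3) × 0.0135 = 0.016164.
- Both donate, co-resident messaged: 0.0135² + 2 × 0.0135 × 0.9865 × 0.3 = 0.0081729. Co-resident not messaged: 0.0135 × (0.01 + 0.99 × 0.3) = 0.0041445.
- Both donate overall: (2/3) × 0.0081729 + (1/3) × 0.0041445 = 0.0068301.
- Co-resident donation among messaged donors: 0.0068301/0.016164 = **42.3%**. With an unmessaged co-resident: 0.0041445/0.0135 = **30.7%**.

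The contrast among donors is 42.3 − 22.1 = 20.2 points, against 30.7 − 1.0 = 29.7 points once messaged co-residents are left out. As a ratio (the scale of a negative binomial model with the usual log link) it is 1.9 against 30.7. The same formulas with other values of r give:

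| r | Control donors, as written | Messaged donors, as written | After exclusion |
|---|---|---|---|
| 0.1 | 9.3% | 16.6% | 1% and 10.9% |
| 0.3 | 22.1% | 42.3% | 1% and 30.7% |
| 0.5 | 31.7% | 62.8% | 1% and 50.5% |

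These rows describe two-patient addresses. Suppose instead that only 20% of patients live at one and the rest live with one resident outside the study who donates at 1%. With r = 0.3, control donors show (0.2 × 0.0027963 + 0.8 × 0.0001)/(0.2 × 0.012673 + 0.8 × 0.01) = 6.1%. Messaged donors show (0.2 × 0.0068301 + 0.8 × 0.0041445)/(0.2 × 0.016164 + 0.8 × 0.0135) = 33.4%. The gap is 27.3 points, close to 29.7, but the ratio is 5.5 rather than 30.7.

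**Analyses 1 and 2.** In the two-patient household with r = 0.3, the Analysis 1 contrast is 0.016164 − 0.012673 = 0.349 points, against 0.35 without spillover. Both arms are lifted almost equally.

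More generally, let h be the share of shortage patients living with one other enrolled shortage patient. Let an exposed control gain a fraction s of the direct effect, and an exposed messaged patient a further fraction t. The share of the effect retained is 1 − (2h/3)(s − t). With h = 20% and s = 0.5:
- t = 0 (a second message adds nothing): 0.933, so 0.327 points and 73.7% power at 1:1.
- t = 0.5 (additive): 1.000.
- t = 1 (mutual reinforcement): 1.067.

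The sign depends on s − t, on which the SAP is silent.

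**The case against.** The strongest reply is that a co-resident's own message is independent of the target's arm, so direct effects balance across the randomised groups and add only noise. For a comparison by group alone this is right. In the example, co-resident donation is (2/3) × 0.0135 + (1/3) × 0.01 = 1.233% for control targets and (2/3) × 0.017495 + (1/3) × 0.01401 = 1.633% for messaged targets. The gap of 0.400 points is spillover. But the SAP's model also conditions on the target's donation, which happens after randomisation, and there the balance is lost.

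It is also fair that the analysis is exploratory, that the SAP says such encouragement may happen rather than that it will, and that the protocol, not shown, may hold a household rule.

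A reader might go further and infer that Analysis 1 is biased toward no effect because controls hear the message second-hand. The SAP does not support that. Its stated mechanism works through donors, about 1% of patients, and raises both arms. Attenuation requires a second message in the home to add less than the first; reinforcement would push the other way.

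Nor does it follow that Analysis 2 is diluted. Both its arms are messaged, and the feature under test is the recipient's own blood type, which a co-resident's message need not share.

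Clustering the main models by address is not needed either if patients are allocated individually. Simulating two-person households, half sharing an identical outcome, with 2:1 allocation and no effect gave an unclustered standard error of 0.00108 against an empirical 0.00106, and a type I error of 4.7%.

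**Conclusion.** The point holds for the household model. As written, it cannot separate donors whom the target recruited from messaged co-residents who recruited the target, and it enters multi-patient addresses more than once. In the illustration the interaction is understated: 20.2 instead of 29.7 points at two-patient addresses, and far more on the ratio scale. The size in this trial depends on the share of multi-patient addresses and on r, neither of which the SAP gives. It also assumes that no household rule exists elsewhere.

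For Analyses 1 and 2 the conclusion is weaker. Any bias is of unknown size and direction. It is negligible if only donors encourage others or if the effect is additive, and runs toward no effect only if a second message in the home adds less than the first. That justifies a robustness check but not a change to the main analyses.

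**What to change.** In the household analysis, do one of the following:
- restrict it to addresses with only one enrolled patient; or
- count as household donors only co-residents who were not sent a study message, including a delayed control message, by the end of the target's 6-week window, and cluster standard errors by address.

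The first is simpler. Neither makes the interaction a randomised comparison, since donor status still follows randomisation, but both remove the route through messaged co-residents.

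Using the same address link, add a robustness check that reruns Analyses 1 and 2 among patients who are the only enrolled patient at their address, a status fixed before any message.

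The cost is SAP wording and a few reruns, with no new data or patients. Project status says that nothing has been analysed and that most outcomes are still to be extracted, so the change can be prespecified. The subset is smaller: at assumed losses of 10% and 20% of patients, 1:1 power for 1% against 1.35% falls from 79.7% to 75.4% and 70.4%. It also leaves out multi-patient households, so it serves only as a check.

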
Project status

The team had originally planned to enroll 20,000 patients per arm, and 80,000 patients total. However, the study team decided to stop the study with just under 15,000 patients per arm due to logistical constraints.

Specifically, reaching the target sample size would have required us to enroll many patients who live far from existing Miller-Keystone donation sites and far from the Danville and Bloomsburg areas where Miller-Keystone often runs blood drives. Due to staffing shortages, it was not feasible to set up the additional blood drives that would have been required to enroll these patients and reach the original target sample size.

As of 4/25/2022, enrollment is complete with eligible patients that live near an existing Miller-Keystone donation site or near Danville or Bloomsburg, where Miller-Keystone ran blood drives for patients in the study. The final sample includes total of 59,093 patients.

The team has extracted primary-outcome data for the first group of participants enrolled. The data were extracted in order to set up a data pulling and sharing protocol with Miller-Keystone. However, these initial data have not yet been analyzed, and data for patients enrolled subsequently have not yet been extracted. Additionally, data collection for some participants is ongoing. We plan to extract the remaining primary outcome data all at once on or after 6/6/2022, 6 weeks following the final message send date (4/25/2022).

With the final sample size of at least 14,772 patients per arm, we will have 80% power to detect an increase in donation rates from 1% to 1.35% between any two study arms, a 35% difference, with a two-tailed alpha of .05. With our original planned sample size of 80,000 patients (~20,000 per arm), we would have had power to detect a smaller increase, from 1% to 1.3%.

Sample and randomization

The sample includes Geisinger patients who have a blood type recorded in their electronic health record, are age 18 or older, and do not have a low hemoglobin test result (<12.5) recorded in the 3 months before the patient list was extracted.

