Analysis 2: We will test the hypothesis that patients who receive the blood-type message will be more likely to donate than those who receive the no-blood-type message by running an OLS regression with a binary predictor variable indicating whether patients were sent the blood-type message or the no-blood-type message.

Notes about timeframes and analysis

Messages sent to patients within a geographic location will be divided into separate message dates so as not to overwhelm appointment scheduling at Miller-Keystone. Timeframes listed above refer to the amount of time elapsed from the send date for a given patient. For instance, the primary outcome timeframe is 6 weeks; thus, for the purposes of this study, a patient will be counted as having donated if they donated blood within 6 weeks of their message send date.

Patients in both control groups will be divided into separate message dates, each assigned to one of the message-date groups for the experimental arms. Each control group will be monitored for appointments and donations during a date range that is aligned with the date range for its corresponding experimental group.

All analyses will exclude patients who scheduled their appointment prior to their message send date.

Sensitivity analyses and robustness checks

The analyses above will be run using a time frame of 6 weeks from the message send date. However, as a robustness check, we will rerun *Analysis 2* on the subset of patients who open the messages, using a time frame of 6 weeks from the date each individual patient opened their message.

We will run an additional robustness check including only patients who scheduled an appointment within the 2 weeks following their message send date.

As another robustness check, we will remove all patients who live within 20 miles of Danville, PA, as these patients are likely to be health care workers. They are therefore more likely to already know their blood type and/or to know their blood type is in short supply.

Recent work suggests that OLS regressions are appropriate in randomized experiments with binary outcome variables such as ours (Gomilla, 2021). However, as a robustness check, we will also run the regressions described above as logistic regressions instead of OLS regressions.

Secondary outcomes

We will use the approaches described in *Analyses 1* and *2* above to evaluate the impact of the intervention on the secondary outcome measures listed in the pre-registration:

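### The exploratory household model adjusts for whether the target patient donated, a result of the message, so neither its group term nor its interaction estimates the randomised effect on household donation

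*SAP*

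**What the plan says.** The analysis is item 1, Household members, under Additional exploratory analyses. Its rationale is that "Patients who donate after receiving messages may also encourage members of their household to donate". The outcome is "the number of donors residing at the same address as each target patient", and a negative binomial regression tests whether it "varies as a function of experimental group, whether the target patient donated or not, and the interaction between these variables". No household model with group alone is listed, and no mediation assumptions, instrumental variable or principal-stratum method is stated.

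Two other parts of the SAP bear on this:

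- **Timing.** Under Notes about timeframes and analysis, "a patient will be counted as having donated if they donated blood within 6 weeks of their message send date". The target's donation is therefore measured after allocation and after the message.
- **Expected effect on donation.** Analysis 1 tests whether "patients who receive a message donate at higher rates than patients who do not receive a message". Analysis 2 tests whether "patients who receive the blood-type message will be more likely to donate than those who receive the no-blood-type message". Donation is the behaviour the messages are meant to change.

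Under Sample and randomization, patients with a needed blood type "will be randomized into the 3 shortage blood-type groups". The no-shortage control group is drawn from patients with other blood types and is not randomised against these three.

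**The concern.** The SAP describes a chain: a message is sent, the target donates, and the target then encourages others at the address. The planned model adjusts for the middle link. This has two consequences.

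- **Real spillover can vanish from the group terms.** If the message reaches the household only through the target's donation, holding that donation fixed removes the effect from both group terms. It moves into the donation coefficient, which compares donors' households with non-donors' households and is not a randomised comparison.
- **Group differences can appear without spillover.** If the message draws in extra donors, the donors in a message arm are not the same kind of people as the donors in the control arm. People who share a home plausibly share an inclination to donate, so the two sets of households may differ for reasons unrelated to any influence of the message on co-residents.

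What is at stake is the reading of one exploratory result. A null group term or interaction could be reported as no household effect, or a reduced interaction as a negative one, when the model estimates neither.

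**Working it through.** **Inputs from the SAP (Project status).** At least 14,772 patients per arm, donation rates of 1% and 1.35%, two-sided alpha 0.05, stated power 80%.

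**Check of those inputs.** The two-proportion power for 14,772 per arm at 1% against 1.35% is 0.797, which agrees with the stated 80%. The SAP gives no figure for the household analysis.

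**Inputs assumed.** Mean household donors per target, by type of target. The SAP gives none, so the values below are for illustration only.

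**Step 1: how different are the donor groups?** Expected donors are 14,772 × 0.01 = 148 in the control arm and 14,772 × 0.0135 = 199 in a message arm. At these rates, and if the message deters nobody, 0.35/1.35 = 26% of message-arm donors would not have donated without it. Targets then fall into three types: would donate anyway (1%), donate only if messaged (0.35%), and do not donate either way (98.65%).

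**Step 2: spillover only through the target's donation.** Assume a base mean of 0.01 household donors, plus 0.20 if the target donates.

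- Control arm: 0.01 + 0.01 × 0.20 = 0.0120. Message arm: 0.01 + 0.0135 × 0.20 = 0.0127. True ratio 0.0127/0.0120 = 1.058.
- Among donors the mean is 0.21 in both arms, and among non-donors 0.01 in both. The planned group term is 1.00 and the interaction 1.00.
- With 0.10 in place of 0.20, the true ratio is 0.01135/0.0110 = 1.03, and both planned terms are again 1.00.

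**Step 3: no spillover, but a shared household inclination to donate.** Assume means of 0.20, 0.05 and 0.01 for the three types, identical in both arms. The true ratio is 1.00.

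- Donors: the message-arm mean is (0.01 × 0.20 + 0.0035 × 0.05)/0.0135 = 0.161, against 0.20 in control. Ratio 0.806.
- Non-donors: the control mean is (0.0035 × 0.05 + 0.9865 × 0.01)/0.99 = 0.01014, against 0.01 in the message arm. Ratio 0.986, which is the group term.
- Interaction ratio: 0.806/0.986 = 0.82.

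Over assumed means of 0.10 to 0.20, 0.01 to 0.10 and 0.01 for the three types, the interaction ratio ran from 0.75 (means 0.20, 0.01, 0.01) to 1.03 (0.10, 0.10, 0.01). The group term ran from 0.97 to 1.00.

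**Step 4: simulation at trial size.** One message arm against control, 14,772 per arm, assumed dispersion 0.5, 400 runs per scenario; median rate ratios.

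- Step 2 scenario (+0.20): planned model group 1.00 and interaction 1.00; group-only model 1.055 (true 1.058), significant in 9% of runs.
- Step 3 scenario: planned model group 0.99 and interaction 0.79, the interaction significant in 8% of runs; group-only model 1.01 (true 1.00).

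**The case against.** The strongest defence has four parts.

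- **The analysis is exploratory and worded as an association.** The SAP never calls these terms randomised effects. This limits the weight of the point but does not answer it: an exploratory analysis should still address its stated question, and the one given is spillover.
- **The question concerns donors' households, so the donation term is deliberate.** That is a fair reading of the intent. However, the terms could be read as direct effects only if nothing unmeasured drove both the target's and the household's donation. The SAP does not claim this, and it is implausible within a home.
- **The sizes rest on assumed household rates.** This stands. The 0.35-point increment is also the difference detectable at 80% power, not a predicted effect; a smaller increment would change the mix of donors less. Under the rates tried, the artefact runs mostly downward, and the group term hardly moves.
- **The group-only model has little power.** This stands too. It averages over about 99% non-donors and detected the assumed spillover in 9% of runs. It corrects what is estimated and does not promise a decisive answer.

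A reader might infer that the planned model is likely to yield a significant false household effect. The working does not support that: the interaction was significant in 8% of runs with no spillover, not far above the nominal 5%. The problem is the quantity estimated, not a large false-positive rate.

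**Conclusion.** The point holds. The only household model conditions on a post-message variable that lies on the pathway it is meant to examine, so its group and interaction terms are not randomised effects on household donation. This conclusion follows from the model as written and does not depend on the assumed rates.

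The sizes do depend on them. With spillover only through donation, both terms are 1.00 against a true ratio of 1.03 to 1.06. With no spillover, the interaction ratio is roughly 0.75 to 1.03. Both use the SAP's 1% and 1.35% with assumed household means.

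No primary or secondary conclusion is affected. A reader might also infer that a control patient's household count includes co-residents who were themselves messaged, and that Analysis 1 should be rerun for contamination. The SAP does not say whether enrolled co-residents are counted and does not report how many addresses hold more than one enrolled patient. It therefore gives no basis for asserting or sizing such an effect, and that inference forms no part of this point.

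**What to change.** - Add a negative binomial model of the number of same-address donors on randomised group alone, limited to the three randomised shortage groups, and name it as the test of household spillover. Report the rate ratio with its confidence interval.
- Keep the planned model with target donation and the interaction, and label it a descriptive association.

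The cost is one extra, simpler model on data the planned analysis already needs. Its drawback is imprecision, so a wide interval around 1 should not be read as absence of spillover. The SAP reports that the outcome data extracted so far have not been analysed and that the rest are still to be extracted, so on that footing the change can be specified before any results are seen.

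### The exploratory OLS test of message group by prior-donor status names no standard error, and the ordinary one gives the wrong error rate when the strata differ in both size and donation rate

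*SAP*

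**What the plan says.** Under *Additional exploratory analyses*, item 2, the SAP gives the aim: "We will evaluate whether message effectiveness differs based on whether the patient has previously donated blood at Miller-Keystone". The method is that "we will run an OLS regression model, testing whether donations vary as a function of experimental group, a bivariate indicator" of earlier donation; the model also contains the product of group and that indicator. Item 3 uses OLS again for geography: "We will test for an interaction between region and experimental group on donation behavior".

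The ground for OLS is in *Sensitivity analyses and robustness checks*: "Recent work suggests that OLS regressions are appropriate in randomized experiments with binary outcome variables such as ours". As a check on that choice, the same section says "we will also run the regressions described above as logistic regressions instead of OLS regressions". The exploratory models come after that sentence.

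No section names a standard error or variance estimator, robust or otherwise. The SAP gives neither the share of prior donors nor their donation rate.

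**The concern.** A binary outcome has variance p(1 − p). At rates near 1% this is almost proportional to p, so a stratum with three times the donation rate has about three times the residual variance. The ordinary OLS standard error pools one variance over all cells. It gives the small stratum and the large stratum the same variance per patient, although the small stratum dominates the variance of the interaction estimate.

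The SAP's two safeguards do not reach this model:

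- The argument for OLS rests on randomisation. Prior-donor status is not randomised, so nothing equalises rates across its strata.
- The logistic check, as worded, covers only regressions placed before it. If it were extended, it would test interaction on the odds scale. That is a different null hypothesis, so it would not repair the OLS test.

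The interaction test is what answers the question in item 2. If prior donors are a minority with a higher rate, which is plausible but an assumption, the ordinary test would report too often that the message works differently in repeat and first-time donors. The sample size does not help, because the ratio of the two variances does not depend on it.

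**Working it through.** **Inputs from the SAP (*Project status*).** Base rate 1%; two-sided alpha 0.05; "With the final sample size of at least 14,772 patients per arm".

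**The plan's own figure.** The SAP claims "80% power to detect an increase in donation rates from 1% to 1.35% between any two study arms". The standard two-proportion formula without continuity correction gives 79.7% power at 14,772 per arm (14,879 would be needed for 80%). The stated figure reproduces, so the 1% rate and group size are used below.

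**Assumed inputs.** Prior-donor share f and rate ratio r (prior donors to others), because the SAP gives neither. Also assumed: no message effect, the same f in each group, overall rate 1%.

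**Formulas.**

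- Rate in others: pn = 0.01 / (1 − f + f·r). Rate in prior donors: pd = r·pn. Variances: vn = pn(1 − pn), vd = pd(1 − pd).
- The interaction is a difference of two risk differences. Its true variance is proportional to vd/f + vn/(1 − f).
- The constant-variance version is proportional to [f·vd + (1 − f)·vn] × [1/f + 1/(1 − f)].
- The group-size factor is common to both and cancels, so a 1:1 and a 1:2 split give the same result.
- The ratio of constant-variance to true variance simplifies to k = [f·vd + (1 − f)·vn] / [(1 − f)·vd + f·vn].
- Numerator minus denominator is (2f − 1)(vd − vn). So k = 1 only if f = 0.5 or the rates are equal. k < 1 (too many rejections) when the smaller stratum has the higher rate. k > 1 (conservative) when the larger one has it.
- Two-group type I error = 2[1 − Φ(1.96·√k)]. Three-group joint 2-df type I error = 0.05^k.

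**Worked case, f = 0.10, r = 2.** pn = 0.01/1.1 = 0.00909 and pd = 0.01818, so vn = 0.00901 and vd = 0.01785. Then k = (0.1 × 0.01785 + 0.9 × 0.00901) / (0.9 × 0.01785 + 0.1 × 0.00901) = 0.00989/0.01697 = 0.583, and √k = 0.764. Two groups: 2[1 − Φ(1.50)] = 13.5%. Three groups: 0.05^0.583 = 17.4%.

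**Type I error of the nominal 5% test, constant-variance standard error:**

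| Prior-donor share | Two groups, r = 2 / 3 / 5 | Three groups, r = 2 / 5 |
|---|---|---|
| 10% | 13.5 / 19.7 / 27.5% | 17.4 / 39.5% |
| 20% | 10.9 / 14.9 / 19.7% | 13.4 / 27.4% |
| 30% | 8.6 / 10.9 / 13.5% | 10.1 / 17.5% |
| 50% | 5.0% at every ratio | 5.0% |
| 70% | 2.5 / 1.7 / 1.0% | 2.0 / 0.6% |

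With equal rates (r = 1) every entry is 5.0%. Smaller ratios do less harm: r = 1.5 gives 9.5% at a 10% share, 7.0% at 30% and 6.0% at 40%. An overall rate of 0.5% or 2% moves the tabulated entries by less than 1 percentage point.

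**Simulation (14,772 per group, 40,000 replicates), constant-variance / HC2:**

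- Two groups: share 10%, r = 2, 13.5% / 4.9%; share 10%, r = 5, 27.5% / 4.9%; share 50%, r = 5, 5.0% / 5.0%; share 70%, r = 5, 1.0% / 5.1%.
- Three groups, joint test: share 10%, r = 5, 39.2% / 5.0%; sparse case with share 3%, r = 2, 20.6% / 5.6%.
- HC3 differs from HC2 by at most 0.1 percentage point.

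**Region model (three groups, joint test, invented layouts), constant-variance / robust:**

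- Size and rate unrelated: 5.4% / 5.7% with five regions, 6.3% / 6.2% with eight.
- Smaller regions with higher rates: 13.0% / 5.5% with five, 13.5% / 6.1% with eight.
- Larger regions with higher rates: 1.8% / 5.8% with five.

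**Analyses 1 and 2.** Each compares two groups through one binary predictor. Under the null the groups share one rate and so one variance, and the ordinary standard error keeps 5%.

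**The case against.** The strongest reply is that the SAP is silent rather than wrong. It fixes an estimator, and OLS is unbiased for the difference in risk differences. An analyst who chose a robust standard error would comply with the text as it stands. The source cited for OLS may also carry a variance estimator, which cannot be settled from the SAP. This stands as a limit: the error arises only if the ordinary standard error is used. It does not remove the point, because the text leaves open a choice that can move the error rate several-fold.

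The magnitude is also assumed. Across the two-group table it runs from 1.0% through 5.0% to 27.5%, so even the direction is unknown. The SAP's exclusion of patients who had booked before their send date could remove some repeat donors and narrow the rate ratio, by an unknown amount. At r = 1.2 the two-group figure is only 5.9% at a 30% share and 5.4% at 40%. All this is fair and is why the figures are given as a range.

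The error rates further assume no message effect, whereas the trial expects one. If messages raised donation by 35% in both strata, with f = 0.10 and r = 5, the additive interaction would really be 0.35 × (0.0357 − 0.0071) ≈ 1 percentage point, and rejecting would not be a false positive. That bears on how an additive interaction is read. A test should still hold its size under its own null.

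Finally, the region layouts are invented, they omit the covariate for donation rates over time that the SAP hopes to add, and they show no material problem when size and rate are unrelated. The region result is therefore conditional only.

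**Conclusion.** The point holds, as a minor one. With the ordinary OLS standard error, the prior-donor interaction test is mis-sized whenever the two strata differ in both size and donation rate. It rejects too often if the smaller stratum has the higher rate and too rarely if the larger one has it. The condition is exact algebra under no message effect and equal stratum shares across groups. The size of the error rests on a prior-donor share and rate ratio that the SAP does not give.

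The region interaction is affected in the same way only if region size and donation rate are related, which the SAP does not say. No primary or secondary conclusion changes through Analyses 1 and 2. What is at stake is an exploratory statement about whether the message works differently in repeat and first-time donors.

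**What to change.** Add one sentence to the SAP: *OLS models, in particular the exploratory interaction models, use heteroskedasticity-robust (HC2 or HC3) standard errors, and joint interaction tests use the same robust covariance.*

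The cost is that sentence and one software option, with no extra data. There is a small downside: with many small regions and few events per cell, the robust joint test can run slightly above nominal. It was about 6% in the eight-region cases, where the smallest cell expects about 6 to 10 events. Results for sparse regions should be read with caution.
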